## 5. EFFICACY

### 5.1. General principles

The primary efficacy analysis will be performed when all participants have reached the Month x (with  $24 \leq x \leq 30$ ) visit or discontinued earlier and the TNI has been reached in the study. Refer to [Figure 1](#) in Section 1.4 for more information on the timing and strategy of statistical testing.

### 5.2. Analysis Specifications

#### 5.2.1. Level of Significance

Unless otherwise stated, all confidence intervals presented will be two-sided at the  $(1 - 2\alpha) \times 100\%$  level with  $\alpha = 0.025$ . The multiple testing strategy is applied by means of fixed sequence testing and is illustrated in [Figure 1](#).

#### 5.2.2. Data Handling Rules

The time between enrollment and the date of HIV-1 infection diagnosis is evaluated for all participants. Enrollment is defined as the date of the first vaccination. Participants becoming HIV infected or dropping out before their Month 7 visit or not having received the first 3 vaccinations within the per protocol specified time window will be excluded from the primary PP analysis. The failure times of participants without HIV-1 infection will be right-censored at the date of the last HIV-1 negative test or at the month 30 visit, whichever occurs earlier. In all interim analyses of VE (eg. for DSMB), participants who have not experienced the primary endpoint will be right-censored at the time of their last HIV-1 negative test.

Dropouts will be right-censored at the time of their last HIV-1 negative test.

### 5.3. Primary Efficacy Endpoint(s)

#### 5.3.1. Definition

The primary efficacy endpoint consists of confirmed HIV-1 infections diagnosed between Month 7 and Month x (with  $24 \leq x \leq 30$ ) visits in the per-protocol (PP) population.

We define the primary vaccine efficacy parameter, i.e.  $VE(7-x)$ , as one minus the probability of the primary efficacy endpoint between month 7 and month x for the vaccine group divided by the probability of the primary efficacy endpoint between month 7 and month x for the placebo group times 100 percent. The Month 7 to Month x vaccine and placebo incidences in the primary VE definition are estimated using cumulative incidences of HIV-1 infection between Months 7 and x obtained from the Nelson-Aalen cumulative hazard function estimator, where:

$$\widehat{VE} = \left(1 - \frac{\widehat{H}_{Vx}(t)}{\widehat{H}_{Pbo}(t)}\right) \times 100\%,$$

with  $\widehat{H}(t)$  the Nelson Aalen estimator of the cumulative incidence in the Vaccine or Placebo arm at time  $t$  (see e.g. Klein and Moeschberger, 1997, p. 83-96). Let

$$\widehat{H}(t) = \sum_{t_i \leq t} \frac{d_i}{Y_i}, \quad \text{with} \quad \widehat{\sigma}_H^2(t) = \sum_{t_i \leq t} \frac{d_i}{Y_i^2},$$

where  $Y_i$  is the number of individuals at risk at time  $t_i$  and  $d_i$  is the number of HIV1-infections at time  $t_i$ .

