11.5.1. Vaccine Efficacy Analysis

The primary analysis of VE will evaluate the number of HIV-1 infections in the vaccine group compared to the number of HIV-1 infections in the placebo group between Month 7 and Month x (with $24 \leq x \leq 30$) in the PP population. The H_0 of VE will be tested $VE(7-x \text{ months}) \leq 20\%$ versus the H_1 $VE(7-x \text{ months}) > 20\%$. Vaccine efficacy is defined as 1-cumulative incidence ratio (vaccine versus placebo) between Month 7 and Month x after first vaccination and is estimated by the transformation of the Nelson-Aalen estimator for the cumulative hazard function. If the lower bound of the 95% CI for $VE(7-x \text{ months})$ is $> 20\%$ (equivalently, the 1-sided p-value for testing $H_0: VE[7-x \text{ months}] \leq 20\%$ is below 0.025), the H_0 will be rejected in favor of the H_1 .

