11.5.1.1. Primary Vaccine Efficacy Analysis: HIV-1 Infection

The primary analysis will be done in the PP population, where participants who become HIV-1 infected or who drop out before Month 7 or who have not received all of the first three vaccinations within the specified time window, will be excluded from the analysis. The date of HIV-1 diagnosis will be the draw date of the first sample that leads to a positive test result by the study protocol's diagnostic algorithm. Dropouts will be censored at the time of their last HIV-1 negative test. To evaluate the primary VE endpoint, the number of HIV-1 infections in the vaccine group will be compared to the number of HIV-1 infections in the placebo group between Month 7 and x months since the first vaccination (with $24 \leq x \leq 30$). The vaccine effect will be assessed using a ratio of

cumulative incidences of HIV-1 infection between Month 7 and x (vaccine versus placebo), estimated using the transformed Nelson-Aalen cumulative hazard function estimator and tested via a Wald test.

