### 1.3. Statistical Hypothesis for Trial Objectives

The primary analysis of VE will evaluate the number of HIV-1 infections in the vaccine group compared to the number of HIV-1 infections in the placebo group between Month 7 and Month x (with  $24 \leq x \leq 30$ ) in the PP population. A description of how x will be determined can be found in Section 1.4 below. The null hypothesis  $H_0: VE(7-x \text{ months}) \leq 20\%$  will be tested against the alternative hypothesis  $H_1: VE(7-x \text{ months}) > 20\%$ . Vaccine efficacy is defined as 1-cumulative incidence ratio (vaccine versus placebo) between Month 7 and Month x after first vaccination, and the cumulative incidence in each group will be estimated using the Nelson-Aalen estimator for the cumulative hazard function. Wald confidence intervals will first be constructed for the log-cumulative incidence ratio, and then, mapped into a confidence interval for VE. If the lower bound of the 95% CI for  $VE(7-x \text{ months})$  is  $> 20\%$  (equivalently, the 1-sided p-value for testing  $H_0: VE[7-x \text{ months}] \leq 20\%$  is below 0.025),  $H_0$  will be rejected in favor of  $H_1$ .

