### 5.3.2. Analysis Methods

VE(7-x) is the target parameter for the primary analysis of overall VE. The primary analysis tests

the null hypothesis  $H_0: VE(7 - x) \leq 20\%$  versus

the alternative hypothesis  $H_1: VE(7 - x) > 20\%$

using a 1-sided 0.025  $\alpha$ -level Wald test of the difference of log cumulative hazard functions at month x for the vaccine group and the control group. See further details in Appendix 1. When the primary analysis is performed at month x (between 24 and 30), the failure times of participants with last HIV-1 negative test at or after the month x visit are right-censored at the right edge of the month x visit window. For participants with last HIV-1 negative test prior to the month x visit and without diagnosis of the HIV-1 infection primary endpoint at or before the month x visit, their failure times are right-censored at the date of the last HIV-negative test.

In addition, to assess potential time-effects of vaccine efficacy, the Nelson-Aalen method will be used to plot the estimated cumulative incidence rates over time for the vaccine and placebo groups. This method will be used to estimate cumulative vaccine efficacy over time, defined as above in 5.3.1, with the method of Parzen, Wei and Ying applied to construct pointwise and simultaneous  $(1 - 2\alpha) \times 100\%$  CIs. In addition, the fluctuations of the instantaneous VE will be visualized graphically (Gilbert, Wei, Kosorok, & Clemens, 2002).

Cox proportional hazards model will also be used for estimating VE(7-x months), measured by one minus the hazard ratio (vaccine versus placebo) and testing whether the VE(7-x months) is  $>$  or  $\leq 20\%$ . For the Cox proportional hazards model, the same censoring will be applied as for the cumulative incidence model used for the primary analysis.

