## 5.4. Secondary Vaccine Efficacy Analyses

### 5.4.1. mITT-2

As a key secondary objective, the VE beyond Month 7 will be evaluated in all participants, regardless of whether they received the first three vaccinations according to the protocol-specified schedule (mITT-2). The secondary endpoint consists of confirmed HIV-1 infections diagnosed between Month 7 and Month x (with  $24 \leq x \leq 30$ ) and vaccine efficacy will be defined as one minus the probability of the secondary efficacy endpoint between month 7 and month x for the vaccine group divided by the probability of the secondary efficacy endpoint between month 7 and month x for the placebo group times 100 percent. The Month 7 to Month x vaccine and placebo incidences in the secondary VE definition are estimated using cumulative incidences of HIV-1 infection between Months 7 and x obtained from the Nelson-Aalen cumulative hazard function estimator, where:

$$\widehat{VE} = \left(1 - \frac{\widehat{H}_{Vx}(t)}{\widehat{H}_{Pbo}(t)}\right) \times 100\%,$$

with  $\widehat{H}(t)$ , the Nelson Aalen estimator of the cumulative incidence in the Vaccine or Placebo arm at time  $t$  (see e.g. Klein and Moeschberger, 1997, p. 83-96). Let

$$\widetilde{H}(t) = \sum_{t_i \leq t} \frac{d_i}{Y_i}, \quad \text{with} \quad \widetilde{\sigma}_H^2(t) = \sum_{t_i \leq t} \frac{d_i}{Y_i^2},$$

where  $Y_i$  is the number of individuals at risk at time  $t_i$  and  $d_i$  is the number of HIV1-infections at time  $t_i$ .

For the analysis of the secondary endpoint in the mITT-2 population, all analysis methods described in Section 5.3.2 will be applied.

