**APPENDIX 1: ADDITIONAL STATISTICAL DETAILS****Analysis primary endpoint****95% Wald confidence interval**

Consider  $\tilde{H}$ , the Nelson Aalen estimator of the cumulative incidence in the Vaccine or Placebo arm (see e.g. Klein and Moeschberger, 2003, p. 83-96):

$$\tilde{H}(t) = \sum_{t_i \leq t} \frac{d_i}{Y_i}, \quad \text{with} \quad \tilde{\sigma}_H^2(t) = \sum_{t_i \leq t} \frac{d_i}{Y_i^2},$$

where  $Y_i$  is the number of individuals at risk at time  $t_i$  and  $d_i$  is the number of HIV1-infections at time  $t_i$ .

Let  $\tilde{H}_{Ratio}(t) = \ln(\frac{\tilde{H}_{VX}(t)}{\tilde{H}_{Pbo}(t)})$ , i.e. natural logarithm of the ratio of the cumulative incidences of the vaccine arm over the placebo arm, with approximate variance:  $\sigma_{H_{Ratio}}^2(t) = \text{var} \left( \ln \left( \frac{\tilde{H}_{VX}(t)}{\tilde{H}_{Pbo}(t)} \right) \right) \approx \frac{\tilde{\sigma}_{H_{Pbo}}^2(t)}{\tilde{H}_{Pbo}(t)^2} + \frac{\tilde{\sigma}_{H_{VX}}^2(t)}{\tilde{H}_{VX}(t)^2}$  resulting in  $(1 - 2\alpha) \times 100\%$  CIs for the VE:

$$\begin{aligned} & [1 - \exp(\tilde{H}_{Ratio}(t) + z_{1-\alpha} \times \sqrt{\sigma_{H_{Ratio}}^2(t)}); \\ & 1 - \exp(\tilde{H}_{Ratio}(t) - z_{1-\alpha} \times \sqrt{\sigma_{H_{Ratio}}^2(t)})], \end{aligned}$$

With  $z_{1-\alpha}$  the  $(1 - \alpha) \times 100\%$ th quantile of the standard normal distribution.

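### SAP 5.3.1 defines VE(7-x) by infection probabilities but prints a ratio of untransformed Nelson-Aalen cumulative hazards; a real mismatch in the primary estimator, with a small numerical effect

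*SAP*

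**What the plan says.** **Definition.** SAP 5.3.1 defines the primary parameter as "one minus the probability of the primary efficacy endpoint between month 7 and month x for the vaccine group" divided by the same probability for placebo. SAP 5.4.1 does the same for the key secondary analysis in mITT-2: "one minus the probability of the secondary efficacy endpoint between month 7 and month x for the vaccine group". Protocol 11.5.1 defines VE by a ratio of cumulative incidences, "estimated by the transformation of the Nelson-Aalen estimator for the cumulative hazard function". Protocol 11.5.1.1 says the cumulative incidences are "estimated using the transformed Nelson-Aalen cumulative hazard function estimator". SAP 1.3 puts the interval on the same scale: "Wald confidence intervals will first be constructed for the log-cumulative incidence ratio".

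**Formula.** SAP 5.3.1 then sets VE = 1 − H_vaccine(t)/H_placebo(t) with H(t) = Σd/Y, and calls H "the Nelson Aalen estimator of the cumulative incidence in the Vaccine or Placebo arm at time" t. SAP 5.4.1 repeats the formula. Appendix 1 builds the confidence interval on the log of H_vaccine/H_placebo, with variance σ²/H² per arm, and describes this as the "natural logarithm of the ratio of the cumulative incidences of the vaccine arm over the placebo arm". SAP 5.3.2 specifies a "Wald test of the difference of log cumulative hazard functions at month x for the vaccine group and the control group". No 1 − exp(−H) step appears anywhere in the SAP.

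**The concern.** Σd/Y estimates the cumulative hazard. The probability of infection by time t is F = 1 − exp(−H), and the ratio of two F values is not the ratio of two H values. As printed, the primary estimator targets a cumulative-hazard ratio. Under proportional hazards that is the quantity the additional Cox analysis in SAP 5.3.2 already targets.

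Three things are at stake:

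- The primary and key secondary estimates would not estimate the parameter that both documents define.
- SAP 1.3 and SAP 5.3.2 name different scales for what should be the same interval and test.
- The point estimate is overstated whenever VE is positive, which bears on a success criterion set at a lower limit of 20%.

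**Working it through.** **1. The plan's own design figures.** Inputs from SAP 1.4 are 1,900 per arm, 5% excluded from PP, 10% annual dropout, 2% annual placebo incidence, VE 20% to Month 7 and 65% afterwards, and follow-up from Month 7 to Month 30 (23 months).

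Take λ = −ln(0.98), δ = −ln(0.90), and exponential times to infection and dropout.

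- At risk at Month 7: 1,900 × 0.95 × exp[−(λ₀ + δ) × 7/12], where λ₀ is λ for placebo and 0.80λ for vaccine. This gives 1,677.5 placebo and 1,681.5 vaccine.
- Infections over 23 months: N₇ × λ₁/(λ₁ + δ) × {1 − exp[−(λ₁ + δ) × 23/12]}, where λ₁ is λ for placebo and 0.35λ for vaccine. This gives 57.7 placebo and 20.5 vaccine, total 78.2.
- Power: Φ[ln(0.80/0.35)/√(1/57.7 + 1/20.5) − 1.96] = 89.5%.

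Across four readings of the annual rates (as hazards or as yearly probabilities), the total is 77.5 to 78.9 and power is 89.2% to 89.8%. The stated 78 infections and approximately 90% power reproduce.

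**2. The gap between the two parameters.** At 2% per year, placebo H = 0.02 × 23/12 = 0.0383 and F = 1 − exp(−0.0383) = 0.0376.

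| Placebo incidence | Hazard VE 65% is, by probability | Hazard VE 20% is, by probability |
|---|---|---|
| 2%/year (design) | 64.56% | 19.69% |
| 4%/year (no-PrEP scenario, SAP 1.4) | 64.12% | 19.39% |
| 6.6%/year (highest rate cited, SAP 1.4) | 63.55% | 19.00% |

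**3. Estimates and 95% intervals.** Assume a mean of N = 1,530 at risk per arm, so H = d/N and Σd/Y² = d/N². This is consistent with the design: 58/1,530 = 0.0379.

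- As written: SE = √(1/d_V + 1/d_P).
- As defined: var(log F) = [exp(−H)/F]² × d/N² per arm.

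For 20 vaccine and 58 placebo infections:

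- H = 0.01307 and 0.03791, and F = 0.01299 and 0.03720.
- As written: VE = 1 − 20/58 = 65.5%, SE 0.2593.
- As defined: VE = 65.1%, SE 0.2568.

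| Vaccine vs placebo infections | As written | As defined |
|---|---|---|
| 20 vs 58 | 65.5% (42.7, 79.3) | 65.1% (42.2, 78.9) |
| 26 vs 52, lower limit | 19.94% | 19.69% |
| 24 vs 49 (total 73), lower limit | 20.18% | 19.94% |
| 33 vs 45, lower limit | −14.92% | −14.73% |
| 34 vs 44, point estimate | 22.7% | 22.5% |

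Doubling the incidence (N = 765) widens the 20 vs 58 point gap from 0.43 to 0.86 points.

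**4. Direction and decisions.** I enumerated every split with a total of 60 to 105 infections, at least 5 in the vaccine arm, and fewer in vaccine than placebo. That is 1,679 splits at N = 1,530.

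- The point estimate is higher as written in all 1,679.
- The lower limit is lower as written in 387. The two lower limits cross at VE 35.6% with 78 infections and 32.3% with 100.
- The decision at 20% changes in 4 splits, all favouring the SAP formula: 19 vs 41, 24 vs 49, 33 vs 63 and 35 vs 66. None has a total of 78.
- With 58 placebo infections, the observed 1 − d_V/d_P needed to clear 20% is 48.6% as written and 48.8% as defined.

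**5. Operating characteristics.** Simulation used 4,000 trials per scenario, 1,677 PP participants per arm, 10% annual dropout, 3-monthly visits, actual Nelson-Aalen risk sets and no interim monitoring.

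- At VE 65% the rejection rate is 92.1% as written and 91.9% as defined, with different decisions in 0.2% of trials.
- At a probability-scale VE of exactly 20% it is 2.65% and 2.60% (Monte Carlo SE 0.25 points).
- A separate simulation in continuous time gave 92.3% and 92.1% (10,000 trials), and 2.54% and 2.44% (20,000 trials).

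Simulated power exceeds the closed form because the normal approximation is rough with about 20 vaccine infections and no monitoring was simulated. This does not affect the comparison between scales.

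**The case against.** The SAP can be read as internally consistent. Section 1.3 says cumulative incidence will be estimated using Nelson-Aalen and names no transformation. Sections 5.3.1 and 5.4.1 and Appendix 1 then use cumulative incidence as their label for H. On that reading the log-cumulative incidence ratio in 1.3 is simply the log of H_vaccine/H_placebo, and an analyst has one estimator and one interval.

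Neither document prints F = 1 − exp(−H). Programming details are deferred to the Data Presentation Specifications, so the program may already transform H. At H of about 0.04 the two scales nearly coincide. The SAP's amendment history lists no change to the VE formula, so replacing it now would itself be an edit after unblinding.

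Several of these points stand. Section 1.3's estimator sentence is ambiguous. The explicit form of F is inferred. What was programmed is unknown, so the finding concerns the plan as written. Nothing shows that the formula was introduced after unblinding.

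They do not remove the mismatch. A loose label for H cannot be squared with a parameter defined by probabilities in 5.3.1 and 5.4.1. The protocol's transformation has to turn a cumulative hazard into a cumulative incidence, and 1 − exp(−H) does that while a logarithm does not. Sections 1.3 and 5.3.2 also name different scales in plain terms.

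**Conclusion.** The concern holds and is minor. The printed primary and key secondary estimator is a cumulative-hazard ratio, whereas the protocol and the SAP's own definition call for a ratio of infection probabilities.

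At design incidence and VE between 20% and 65%, the formula raises the point estimate by about 0.2 to 0.4 points. The gap reaches about 1.5 points (65% against 63.55%) at the highest incidence the documents cite. The lower limit moves by at most about 0.4 points at 78 infections. It moves in the vaccine's favour above a VE of about 36% and against it below that. The sample size, target number of infections, power and error rate need no revision.

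The closed-form figures rest on the assumed 1,530 at risk per arm (765 for doubled incidence), and the simulations omit interim monitoring. The textual contradiction depends on neither.

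**What to change.** - In SAP 5.3.1, 5.4.1 and Appendix 1, set F(t) = 1 − exp(−H(t)) and VE = 1 − F_vaccine/F_placebo, with var(log F) = [exp(−H)/F]² × Σd/Y² per arm.
- In 5.3.2, change the test to a difference of log cumulative incidences.
- Keep the cumulative-hazard-ratio result as a labelled sensitivity analysis, and state in the report which estimator the program used.

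Relabelling the parameter as a cumulative-hazard ratio would also end the contradiction. However, it would depart from the protocol's parameter in a SAP whose versions 1.2 and 1.3 postdate the study-level unblinding of 18 January 2023. Conforming to the protocol is easier to defend, and reporting both versions answers the worry about a late edit.

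The cost is three formula corrections, one phrase and, if the program follows the printed formula, a small programming change. The point estimate and lower limit would shift by the amounts given above.

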### 5.3.2. Analysis Methods

VE(7-x) is the target parameter for the primary analysis of overall VE. The primary analysis tests

the null hypothesis  $H_0: VE(7 - x) \leq 20\%$  versus

the alternative hypothesis  $H_1: VE(7 - x) > 20\%$

using a 1-sided 0.025  $\alpha$ -level Wald test of the difference of log cumulative hazard functions at month x for the vaccine group and the control group. See further details in Appendix 1. When the primary analysis is performed at month x (between 24 and 30), the failure times of participants with last HIV-1 negative test at or after the month x visit are right-censored at the right edge of the month x visit window. For participants with last HIV-1 negative test prior to the month x visit and without diagnosis of the HIV-1 infection primary endpoint at or before the month x visit, their failure times are right-censored at the date of the last HIV-negative test.

In addition, to assess potential time-effects of vaccine efficacy, the Nelson-Aalen method will be used to plot the estimated cumulative incidence rates over time for the vaccine and placebo groups. This method will be used to estimate cumulative vaccine efficacy over time, defined as above in 5.3.1, with the method of Parzen, Wei and Ying applied to construct pointwise and simultaneous  $(1 - 2\alpha) \times 100\%$  CIs. In addition, the fluctuations of the instantaneous VE will be visualized graphically (Gilbert, Wei, Kosorok, & Clemens, 2002).

Cox proportional hazards model will also be used for estimating VE(7-x months), measured by one minus the hazard ratio (vaccine versus placebo) and testing whether the VE(7-x months) is  $>$  or  $\leq 20\%$ . For the Cox proportional hazards model, the same censoring will be applied as for the cumulative incidence model used for the primary analysis.

## 5.4. Secondary Vaccine Efficacy Analyses

### 5.4.1. mITT-2

As a key secondary objective, the VE beyond Month 7 will be evaluated in all participants, regardless of whether they received the first three vaccinations according to the protocol-specified schedule (mITT-2). The secondary endpoint consists of confirmed HIV-1 infections diagnosed between Month 7 and Month x (with  $24 \leq x \leq 30$ ) and vaccine efficacy will be defined as one minus the probability of the secondary efficacy endpoint between month 7 and month x for the vaccine group divided by the probability of the secondary efficacy endpoint between month 7 and month x for the placebo group times 100 percent. The Month 7 to Month x vaccine and placebo incidences in the secondary VE definition are estimated using cumulative incidences of HIV-1 infection between Months 7 and x obtained from the Nelson-Aalen cumulative hazard function estimator, where:

$$\widehat{VE} = \left(1 - \frac{\widehat{H}_{Vx}(t)}{\widehat{H}_{Pbo}(t)}\right) \times 100\%,$$

with  $\widehat{H}(t)$ , the Nelson Aalen estimator of the cumulative incidence in the Vaccine or Placebo arm at time  $t$  (see e.g. Klein and Moeschberger, 1997, p. 83-96). Let

$$\widetilde{H}(t) = \sum_{t_i \leq t} \frac{d_i}{Y_i}, \quad \text{with} \quad \widetilde{\sigma}_H^2(t) = \sum_{t_i \leq t} \frac{d_i}{Y_i^2},$$

where  $Y_i$  is the number of individuals at risk at time  $t_i$  and  $d_i$  is the number of HIV1-infections at time  $t_i$ .

For the analysis of the secondary endpoint in the mITT-2 population, all analysis methods described in Section 5.3.2 will be applied.

#### 5.4.2. Other vaccine efficacy analyses

##### 5.4.2.1. Time intervals

Other secondary objectives will evaluate the VE over different time intervals at least VE[0-x months] and VE[13-x months]), but will not anymore be assessed by 6-monthly time intervals.

##### 5.4.2.2. Analysis Sets

VE in different analysis sets (eg, mITT, mITT3, FIS), using similar methods as described in Section 5.4 will also be evaluated.

